1.5. Potential Risks and Benefits of the Treatment Regimen

INCB050465 has effects on the immune system. Therefore, subjects in this study will be monitored closely for evidence of infections or new cancers, and study treatment administration will be discontinued if there is evidence of clinically significant infection or new cancer.

While PJP has not been reported with the use of INCB050465 either as monotherapy or in combination therapy, subjects who receive INCB050465 in this study will receive PJP prophylaxis. Subjects will be asked to report all sulfa drug allergies and those allergic to standard PJP prophylaxis with sulfonamide antibiotics will receive either inhaled pentamidine or atovaquone for PJP prophylaxis; these subjects will not be given dapsone.

As presented in Section 1.3, the most common AEs ($\geq 20\%$) observed with INCB050465 monotherapy have been nausea, diarrhea, fatigue, cough, rash, and vomiting. Serious AEs (≥ 2 subjects) have included colitis, diarrhea, sepsis, hypotension, ventricular tachycardia, pyrexia, respiratory failure, pneumonia, bronchitis, exfoliative dermatitis, syncope, urinary tract infection, and bacteremia. Dose modification guidance and supportive care guidelines for diarrhea/colitis are implemented in this study.

Based on efficacy and safety data from the ongoing Study INCB 50465-101, which evaluated a continuous 20 mg QD dose regimen, the treatment regimen for Study INCB 50465-204 will be 20 mg QD for 8 weeks, followed by either 20 mg once weekly or 2.5 mg QD of INCB050465. As detailed in Section 1.3, these regimens are proposed to assess whether the frequency of AEs leading to treatment withdrawal will be reduced while maintaining PI3K pathway inhibition and maintenance of response.

INCB050465 is metabolized primarily by CYP3A4; therefore, use of any potent CYP3A4 inhibitors or inducers within 14 days or 5 half-lives (whichever is longer) before the first dose of INCB050465 will be prohibited.

The effects of INCB050465 on fetal development has not been evaluated nor is it known whether INCB050465 passes into human breast milk; therefore, subjects who are pregnant or breastfeeding are excluded from participation in this study.

There are no preclinical data available to date on the potential phototoxicity of INCB050465. Therefore, subjects enrolled in this study taking INCB050465 will be instructed by the site staff

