11. Use or expected use during the study of any prohibited medications, including potent CYP3A4 inhibitors or inducers (see [Appendix D](#)), within 14 days or 5 half-lives (whichever is longer) before the date of study treatment administration.
12. Significant concurrent, uncontrolled medical condition, including, but not limited to, renal, hepatic, hematological, GI, endocrine, pulmonary, neurological, cerebral, or psychiatric disease.
13. Current or previous other malignancy within 3 years of study entry, except cured basal or squamous cell skin cancer, superficial bladder cancer, prostate intraepithelial neoplasm, carcinoma *in situ* of the cervix, or other noninvasive or indolent malignancy without sponsor approval.
14. History of stroke or intracranial hemorrhage within 6 months of the date of study treatment administration.
15. Chronic or current active infectious disease requiring systemic antibiotics, antifungal, or antiviral treatment or exposure to a live vaccine within 30 days of dosing.
16. Known HIV infection or positivity on immunoassay. **Note:** HIV screening test is optional for subjects enrolled in the United States, but subjects with known HIV infection in the United States will be excluded.
17. Liver disease: HBV or HCV infection: Subjects positive for HBsAg or hepatitis B core antibody will be eligible if they are negative for HBV-DNA; these subjects should be considered for prophylactic antiviral therapy. Subjects positive for anti-HCV antibody will be eligible if they are negative for HCV-RNA.
18. Clinically significant cardiac disease, including unstable angina, acute myocardial infarction, and/or cardiac conduction issues within 6 months of the date of study treatment administration.
19. Current New York Heart Association Class II to IV congestive heart failure or uncontrolled arrhythmia.
20. Presence of an abnormal ECG that is clinically meaningful. Screening QTc interval > 450 milliseconds is excluded (corrected by Fridericia). In the event that a single QTc is > 450 milliseconds, the subject may enroll if the average QTc for 3 ECGs is < 450 milliseconds.
21. Unable to swallow and retain oral medication, malabsorption syndrome, disease significantly affecting GI function, total resection of the stomach or small bowel, ulcerative colitis, symptomatic inflammatory bowel disease, or partial or complete bowel obstruction.
22. Known hypersensitivity or severe reaction to INCB050465 or its excipients (see [IB](#)).

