5.4.1.1. Dose Modifications

Dose modification guidance for AEs that have been previously observed in subjects receiving INCB050465 or are potential class-effect AEs are provided (see [Table 3](#) and [Table 5](#)). The starting dose and dose reduction levels of INCB050465 are provided (see [Table 4](#)). Individual decisions regarding dose interruption and reduction should be made using clinical judgment and in consultation with the sponsor's medical monitor, taking into account relatedness of the AE to the study treatment and the subject's underlying condition. Adverse events that have a clear alternative explanation or transient (≤ 72 hours) abnormal laboratory values without associated clinically significant signs or symptoms may be exempt from dose reduction guidelines.

Table 3: Guidelines for Interruption and Restarting INCB050465

ADVERSE EVENT	ACTION TAKEN
Chemistry	

 Grade 3 AST and/or ALT ($> 5.0 \times \text{ULN}$). 
Note: In subjects with liver metastasis-related elevations at baseline, contact sponsor to discuss clinical management and possible dose reductions.
	
Step 1: Interrupt INCB050465 and monitor weekly until the toxicity has resolved to \leq Grade 1.
 
Step 2: Restart INCB050465 at next lower dose with medical monitor approval. Monitor as clinically indicated.

Hematology	

 Grade 3 ANC ($< 1.0 \times 10^9/\text{L}$). Grade 2 platelet count (50 to $< 75 \times 10^9/\text{L}$) for subjects who enrolled with platelets $> 100 \times 10^9/\text{L}$. Grade 3 platelet count ($< 50 \times 10^9/\text{L}$) for subjects who enrolled with platelets $\leq 100 \times 10^9/\text{L}$. 	
Step 1: Interrupt INCB050465 up to 14 days until the toxicity has resolved to \leq Grade 1 or pretherapy baseline. For Grade 3 ANC, monitor at least weekly.
 
Step 2: Restart INCB050465 at same dose; monitor as clinically indicated.

 Grade 4 ANC ($< 0.5 \times 10^9/\text{L}$). Grade 3 or Grade 4 febrile neutropenia. Platelet count is Grade 4 ($< 25 \times 10^9/\text{L}$). 	
Step 1: Interrupt INCB050465 up to 14 days until the toxicity has resolved \leq Grade 2. (Monitor at least weekly.)
 
Step 2: Restart INCB050465 at same dose. Monitor as clinically indicated. If reoccurs, restart at next lower dose.

Other toxicities	

 Diarrhea/colitis. 	See Table 5 .

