
 Pneumonitis (Grade 1). 	
Step 1: Interrupt INCB050465 until the toxicity has resolved.
 
Step 2: Restart INCB050465 at next lower dose. Monitor as clinically indicated.

 Pneumonitis (Grade ≥ 2). 	Permanently discontinue INCB050465.

 Skin toxicity (eg, rash, pruritus, unless otherwise specified; Grade 2 and 3). 	
Step 1: Interrupt INCB050465 until the toxicity has resolved to \leq Grade 1.
 
Step 2: Restart INCB050465 at same dose. If assessed as related to INCB050465, restart at next lower dose.

 Exfoliative dermatitis (Grade 1). 	
Step 1: Interrupt INCB050465 until the toxicity has resolved.
 
Step 2: Restart INCB050465 at next lower dose. Monitor as clinically indicated.

 Exfoliative dermatitis (\geq Grade 2). 	Permanently discontinue INCB050465.

 Intestinal perforation (any grade). 	Permanently discontinue INCB050465.

 PJP infection. 	Interrupt INCB050465. Permanently discontinue INCB050465 if PJP infection is confirmed.

 CMV infection. 	Subjects with CMV viremia without associated clinical signs of CMV infection should be carefully monitored. Consider interrupting INCB050465 for subjects with CMV viremia and clinical signs of infection until the infection has resolved. Restart INCB050465 reduced by 1 dose level if approved by the medical monitor.

Table 3: Guidelines for Interruption and Restarting INCB050465 (Continued)

ADVERSE EVENT	ACTION TAKEN
• Varicella zoster infection.	Interrupt INCB050465. Restart INCB050465 only by approval of the medical monitor.
• Any Grade 1 or Grade 2 toxicity unless otherwise specified.	Continue INCB050465 and treat the toxicity; monitor as clinically indicated.
• Any Grade 3 toxicity, if clinically significant and not manageable by supportive care unless otherwise specified.	Step 1: Interrupt INCB050465 up to 14 days until the toxicity has resolved to \leq Grade 1. Step 2: Restart INCB050465 at same dose. If assessed as related to INCB050465, restart at next lower dose. If interrupted for > 14 days, contact the medical monitor for approval to restart INCB050465. Monitor as clinically indicated.

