• Any recurrent Grade 3 toxicity after 2 dose reductions.	Discontinue INCB050465 administration and follow-up per Protocol. Exceptions require approval of sponsor.
• Any other Grade 4 toxicity.	Discontinue INCB050465 administration and follow-up per Protocol. Exceptions require approval of sponsor.

ALT = alanine aminotransferase; AST = aspartate aminotransferase; CMV = cytomegalovirus; IV = intravenous; ULN = upper limit of normal.

Table 4: Dose Levels and Reductions for INCB050465

Timepoint	Treatment A	Treatment B
Starting dose	20 mg QD for 8 weeks (Day 1 through Day 56)	20 mg QD for 8 weeks (Day 1 through Day 56)
First dose reduction	10 mg QD	10 mg QD
Second dose reduction	5 mg QD	5 mg QD
Week 9 (Day 57) onward	20 mg once weekly ^a	2.5 mg QD ^b
First dose reduction	10 mg once weekly	1 mg QD ^c
Second dose reduction	5 mg once weekly	NA

^a All subjects will receive 20 mg once weekly at Week 9 (Day 57) regardless of prior dose level, unless a dose modification of a switch to a QW schedule before Week 9 is required for diarrhea/colitis management (see Table 5).

^b All subjects will receive 2.5 mg QD at Week 9 (Day 57) regardless of prior dose level, unless a dose modification of a switch to a QW schedule is required for diarrhea/colitis management (see Table 5).

^c Further dose modification due to diarrhea or colitis for subjects on 1 mg QD is permitted (see Table 5).

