6. STUDY ASSESSMENTS

All study assessments will be performed as indicated in the schedule of assessments ([Table 6](#)), and all laboratory assessments will be performed as indicated in [Table 7](#). All assessments mandated throughout the study must be performed on a calendar schedule; delays in treatment administration will not delay performance of assessments. By convention, Week 4, Week 8, Week 12, etc, means the completion of 4, 8, or 12 weeks, respectively. [Table 8](#) presents a summary of clinical laboratory analytes to be assessed. The order of assessments is suggested by the order of mention within the schedule of assessments. See [Section 7](#) for instructions on each assessment.

Table 6: Schedule of Assessments

Procedure	Section	Screening	Treatment			EOT	Follow-Up		
		Days -28 to -1	Day 1 ^a	Every 4 Weeks Through Week 48 (± 3 Days)	Every 12 Weeks From Week 48 (± 1 Week)		Safety	Disease	Survival
							EOT + 30-35 Days		Every 12 Weeks (± 1 Week)
Informed consent	7.1	X							
Contact IWRS	7.2	X	X	X	X	X			
Inclusion and exclusion criteria	3	X	X						
Demography and medical history	7.3	X							
Prior/concomitant medications	7.4	X	X	X	X	X	X		
AE assessment ^d	8.1	X	X	X	X	X	X		
Comprehensive physical exam	7.5.2	X ^e				X			
Disease-specific physical exam	7.5.3		X	X	X		X		
Vital signs	7.5.4	X	X	X	X	X	X		
12-lead ECG	7.5.5	X	X ^f	X ^f	X	X	X		
ECOG performance status	7.5.6	X	X	X	X	X	X		
CT/MRI scan	7.6.1	X		Every 8 weeks through Week 24 (± 1 week), then every 12 weeks through Week 96, and then every 24 weeks thereafter until PD				X ^e	
Bone marrow exam	7.6.2	X ^g			X ^h			X ^h	
Prophylactic treatment for PJP	5.6.1			X ⁱ					
Study treatment dispensing	5.1.1		X	X	X				
Study treatment compliance	5.3		X	X	X	X			
INCB050465 administration	5.2.1		X	X	X				
Disease follow-up	6.4.2							X ^e	
Survival follow-up	6.4.3							X ^j	

^a All procedures are to be performed before administration of study treatment on Day 1.

^d Adverse events will be monitored from the time the subject signs the ICF until at least 30 days after the last dose of study treatment. Serious AEs occurring more than 30 days after the last dose of study treatment should be reported to the sponsor or its designee if the investigator suspects a causal relationship to the study treatment. Once detected, AEs should be followed until resolved or judged to be permanent.

^e Height required at screening only.

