^f Timed triplicate ECGs will be obtained during the Day 1 visit (predose) and Week 4 visit (predose and 1.5 hours [\pm 15 minutes] after receiving study treatment).

^g Required at baseline except for reasons provided in Section 7.6.2.

^h If disease is present in bone marrow at baseline, a bone marrow biopsy will be required to confirm CR or may be performed as clinically indicated. For subjects with splenic MZL without measurable disease (ie, only have histologically confirmed bone marrow infiltration), a bone marrow biopsy/examination must be performed when the number of lymphocytes in the blood normalize.

ⁱ *Pneumocystis jirovecii* pneumonia prophylaxis should be given while subjects are receiving study treatment and continue for at least 2 to 6 months after the last dose of study treatment.

^j May be conducted by clinic visit, telephone, or email.

Table 7: Schedule of Laboratory Assessments

Laboratory Tests ^a	Section	Screening	Treatment				EOT	Safety Follow-Up
		Day -28 to -1	Day 1 ^b	Every 4 Weeks Through Week 48 (± 3 Days)	Every 12 Weeks From Week 48 (± 1 Week)	Other		EOT + 30-35 Days
Serum chemistries	7.5.7.1	X	X ^c	X	X		X	X
Hematology ^d	7.5.7.1	X	X ^c	X	X	X ^e	X	X
Serology	7.5.7.3	X		X ^f	X ^f			
HIV testing	7.5.7.3.1	X ^g						
Serum pregnancy	7.5.7.2	X ^h					X	
Urine pregnancy	7.5.7.2					X ⁱ		
Tumor/bone marrow biopsy	7.8.5	X ^m				X ⁿ		

^a All laboratory assessments must be performed at a central laboratory, unless otherwise specified (see Section 7.5.7).

^b All laboratory assessments are to be performed before administration of study treatment on Day 1, unless otherwise specified.

^c If chemistry and/or hematology laboratory assessments occurred in the preceding 7 days, Day 1 assessments may be omitted.

^d Hematology will be collected every 2 weeks for the first 8 weeks.

^e Week 2 (Day 15) and Week 6 (Day 43) ± 3 days.

^f Samples for CMV DNA analysis only.

^g Optional for subjects enrolled in the United States.

^h Only for females of childbearing potential; negative serum pregnancy test must be obtained within 14 days before administration of study treatment. Screening test may be performed centrally or at the investigative site laboratory.

ⁱ Only for females of childbearing potential; if a urine pregnancy test is positive, then a serum pregnancy test should be performed. Urine pregnancy must be collected every 4 weeks until last dose of study treatment.

[REDACTED]

Table 8: Laboratory Tests: Required Analytes

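### Subjects positive for HBsAg or hepatitis B core antibody enter on one negative HBV-DNA, with no later HBV-DNA test scheduled and no HBV rule in Table 3

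*Protocol*

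**What the plan says.** **Entry.** Criterion 17 in Protocol Section 3.2 reads: "Subjects positive for HBsAg or hepatitis B core antibody will be eligible if they are negative for HBV-DNA". It adds that antiviral prophylaxis should be considered in these subjects, but does not require it. Screening serology, which includes HBV-DNA (Table 8), is used for eligibility (Section 6.1).

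**Testing afterwards.** The serology row of Table 7 is marked in the 4-weekly and 12-weekly treatment columns. Both marks carry footnote f: "Samples for CMV DNA analysis only". The row has no mark at EOT or safety follow-up. Section 7.5.7.3 refers back to the tables and adds no schedule.

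**Action rules.** Section 5.4.1.1 gives the scope of Table 3: "Dose modification guidance for AEs that have been previously observed in subjects receiving INCB050465 or are potential class-effect AEs are provided". The table has rows for PJP, CMV and varicella zoster infection, and none for HBV. The rows that would apply to a rise in liver enzymes are:
- Grade 1 or 2 toxicity not otherwise listed: "Continue INCB050465 and treat the toxicity; monitor as clinically indicated".
- Grade 3 AST/ALT: interrupt, monitor weekly until Grade 1 or lower, then "Restart INCB050465 at next lower dose with medical monitor approval".
- Any other Grade 4 toxicity: "Discontinue INCB050465 administration and follow-up per Protocol", with exceptions if the sponsor approves.

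Section 1.5 adds a general rule: "study treatment administration will be discontinued if there is evidence of clinically significant infection or new cancer". HBV is in neither list of adverse events of special interest (Protocol Section 8.5, SAP Section 9.2.2).

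**The concern.** The protocol knowingly enrols people with serological evidence of hepatitis B and treats their risk as settled by one screening result. Its own text suggests the risk continues. It raises antiviral prophylaxis for this group, says in Section 1.5 that the drug affects the immune system, requires prior anti-CD20 therapy (Section 3.1), and directs steroids for diarrhea and colitis (Table 5). A site that follows Table 7 as written will never repeat the HBV-DNA test. Reactivation would then show first as liver injury, and drug could continue or be restarted before the cause was known. What is at stake is the safety of these subjects; the response-rate analysis does not depend on it.

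**Working it through.** The plan gives no figure to reproduce, so the check sets the entry rule beside the schedule and the action rules.

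**1. HBV-DNA tests scheduled after screening.**
- Serology marks at Weeks 4, 8, ..., 48: 48 / 4 = 12.
- Serology marks at Weeks 60, 72, 84, 96: 4.
- Total through Week 96: 12 + 4 = 16, all limited to CMV DNA by footnote f.
- EOT and safety follow-up: 0.
- HBV-DNA tests: 0 of 16. Other rows of Table 7 are redacted, but this row and its footnote are legible, so redaction does not explain the gap.

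**2. An ALT rise in a seropositive subject under Table 3.** At Grade 1 or 2, drug continues. At Grade 3 (above 5 x ULN), drug stops, ALT is followed weekly to Grade 1 or lower, and drug can restart one level down if the medical monitor agrees. At Grade 4, drug is discontinued. No step asks for HBV-DNA. The stop in Section 1.5 needs evidence of infection, which no scheduled test would supply.

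**3. The grounds for admission.** Appendix E (Amendment 1) gives two: no reported HBV or HCV reactivation in Study INCB 50465-101, and alignment with approved PI3K inhibitors. The second cannot be checked from these documents. On the first, Section 1.3 reports 72 subjects with a median of 122.5 days on treatment, against about 52 weeks expected here: 52 x 7 = 364 days, and 364 / 122.5 = 3.0 times longer. The number of seropositive subjects in that study is not given. With zero events in n subjects, the one-sided 95% upper bound is 1 - 0.05^(1/n):
- n = 72 (assumption: all seropositive): 1 - 0.05^(1/72) = 4.1%.
- n = 10 (assumption, for illustration): 1 - 0.05^(1/10) = 25.9%.

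So the absence of events does not exclude a risk worth monitoring. Both grounds also concern who may enter, not how they are followed.

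**4. Longest gaps if HBV-DNA is added to the existing draws.** Section 6 states: "By convention, Week 4, Week 8, Week 12, etc, means the completion of 4, 8, or 12 weeks, respectively", so Week 4 is Day 29. Windows are 3 days either side through Week 48 and 1 week either side after that.
- Screening to Week 4: Day -28 to Day 29 + 3 = Day 32. With no Day 0, 28 + 31 = 59 days.
- Later draws through Week 48: 28 + 3 + 3 = 34 days.
- Week 48 to Week 60: 84 + 3 + 7 = 94 days.
- After Week 60: 84 + 7 + 7 = 98 days, or 14 weeks.

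ALT/AST follow the same treatment-visit columns, so after Week 60 even the present indirect signal can be 14 weeks apart.

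**The case against.** The strongest reply is that the documents never name HBV reactivation as a risk of this drug or of its class, and none was reported in the earlier study. Table 3 covers observed or potential class-effect events, so the missing row fits its stated scope. That stands to this extent: the plan does not contradict itself. It does not justify having no test. Section 1.5 says PJP had not been reported with the drug either, yet PJP has mandatory prophylaxis and a Table 3 row.

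A second reply lists existing cover:
- ALT, AST and bilirubin every 4 weeks through Week 48;
- ALT/AST of at least 5 x ULN as events of special interest (Section 8.5);
- resolution to Grade 1 or lower before restart;
- individual clinical judgment that takes account of underlying disease (Section 5.4.1.1);
- viral causes to be ruled out for suspected immune-related events (Section 5.4.4);
- extra tests by agreement (Table 8 note) and unscheduled visits (Section 6.6);
- IDMC review;
- the potential Hy's law listing (SAP Section 9.3.3), which is reporting only.

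These are real and reduce the severity, but none requires HBV-DNA. Criterion 15, which excludes infection needing antiviral treatment, may also narrow the HBsAg-positive group.

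A third reply is that anti-HCV-positive, HCV-RNA-negative subjects are admitted in the same way with no later RNA test. That is true. The reason to put HBV first is in criterion 17 itself, which raises antiviral prophylaxis only for the HBV group.

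Finally, the number of seropositive subjects is unknown and could be zero, and the fix still leaves gaps of 94 to 98 days after Week 48. Both points are correct.

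**Conclusion.** The concern holds. Subjects known to be positive for HBsAg or core antibody are admitted on one negative HBV-DNA; none of the 16 later serology draws through Week 96 includes that test; and no Table 3 rule refers to HBV. The sponsor should correct this, as a gap in safety monitoring with partial indirect cover. No count of affected subjects or of harm can be given, because the documents do not say how many seropositive subjects are enrolled or how often reactivation occurs. The day counts assume that visits fall at the extremes of their windows. Sites may already test under local practice, but the protocol does not ask them to.

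**What to change.** 1. **Table 7, footnote f.** Replace with: *Samples for CMV DNA analysis; in subjects positive for HBsAg or hepatitis B core antibody at screening, also HBV-DNA.*
2. **Table 7, serology row (preferable).** Add marks at EOT and Safety Follow-Up, where blood is already drawn, with the footnote: *HBV-DNA only, in subjects positive for HBsAg or hepatitis B core antibody at screening.*
3. **Table 3, new row.** *HBV-DNA newly detectable: contact the medical monitor promptly. Antiviral therapy and interruption of INCB050465 according to clinical judgment and institutional guidelines.*
4. **Table 3, Grade 3 AST/ALT, Step 2.** Add: *In subjects positive for HBsAg or hepatitis B core antibody at screening, do not restart without an HBV-DNA result.* A positive result then goes to the medical monitor, who must already approve restart.

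Criterion 15 stays as it is. As a clerical matter, the synopsis line on liver disease can point to criterion 17 for the exceptions.

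**Cost.** One protocol amendment, with IRB/IEC approval across about 100 planned sites. Per seropositive subject, up to 12 assays through Week 48, 4 more through Week 96, and up to 2 at EOT and safety follow-up; over the expected 52 weeks of treatment this is 12 + 2 = 14. HBV-DNA is already a Table 8 analyte and goes onto existing draws, so there are no new visits and no change in eligibility. Low-level or transient positives will add some medical monitor reviews. The edits can also cover subjects already enrolled and still on treatment.
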